8.5 Safety Analyses

8.5.1 Extent of Exposure

The extent of study medication exposure will be listed for each subject as the number of days on study medication, and summary statistics will be provided for each treatment group. Duration of exposure (in days) will be calculated as (last dose date – first dose date + 1).

The extent of exposure for each treatment group will also be summarized categorically. The categories of exposure are defined as follows: exposures of ≥ 13 weeks, ≥ 26 weeks, ≥ 39 weeks, ≥ 52 weeks, ≥ 65 weeks and ≥ 78 weeks.

8.5.2 Adverse Events

Adverse event tables will include summaries of TEAEs by treatment arms. A TEAE is defined as any new AE that begins, or any preexisting condition that worsens in severity, after at least one dose of study treatment has been administered.

An overview table containing the number and percent of the following will be included and presented by treatment arms:

- Number of total AEs, TEAEs, and deaths
- Incidence of patients with at least one TEAE, drug-related TEAE, serious AE (SAE), drug-related SAE, and non-serious TEAEs
- Incidence of patients who discontinued due to TEAE, drug-related TEAE, SAE, and drug-related SAE
- Incidence of deaths and deaths due to drug-related TEAE

The following tabular summaries of TEAEs will be provided by treatment arms:

- TEAEs summarized by SOC and PT, descending frequency of PT, by maximum severity, by age group (50-65 inclusive, > 65 years), and by disease stage (MCI, Mild AD).
- Adverse events leading to discontinuation summarized by SOC and PT, and by descending frequency of PT.
- Drug-related AEs summarized by SOC and PT, and by descending frequency of PT.
- Serious adverse events summarized by SOC and PT, descending frequency of PT, and will include a summary of drug related events.
- SAE will also be summarized by age groups and by disease stage (as defined above).

MRI Safety Analsyes

The safety assessments will also include analyses of MRI findings (ARIA-E and ARIA-H) based on the central MRI readings by treatment arms.

Below are the rules to follow for AE summaries:

- A drug-related AE is defined as an AE with an assigned relationship of "possibly related," "probably related," "definitely related," or missing.
- When assessing severity, the TEAE with the worst severity will be chosen for a subject.
- AEs with missing severity will be summarized and presented separately.

AEs will be coded using most current Medical Dictionary for Regulatory Activities (MedDRA) version.

8.5.3 Evaluation of ARIA on Brain MRI

Evaluation of amyloid-related imaging abnormalities or ARIA on Safety MRIs (Sperling 2011) will include evaluation of ARIA-E (brain edema or effusion), ARIA-H (microhemorrhages), ARIA-H (superficial siderosis) and ARIA-H (macrohemorrhages). Safety MRIs will also be analyzed for severity of white matter disease (WMD) in the periventricular and deep white matter, using the Fazekas severity scores. Other ischemic abnormalities such as lacunes or infarcts will also be evaluated. Shift tables for the 4 types of ARIA, WMD parameters and the other ischemic lesions will be provided by visit. Continuous variables for the ARIA-H will also be summarized by visit.

Drug Suspension due to MRI Findings

Some subjects who develop MRI findings of interest may be instructed to suspend study drug till resolution of the MRI finding. The number of subjects whose study drug was suspended by the Sponsor or investigator for MRI finding, and the reason for study drug suspension [ARIA-

E or ARIA-H with macrohemorrhage or ARIA-H with siderosis, or a combination of these lesions)] will also be summarized.

Clinical Laboratory Evaluations

Clinical lab results will be reported for hematology, clinical chemistry, coagulation tests, and urinalysis and will be summarized by visit.

Parameters will be summarized descriptively through change from baseline (CFBL) and percent CFBL for numeric values. If a parameter is categorical, it will be listed only.

Out-of-range values will be assessed through shift tables. Each lab value will be assessed as low, normal or high based on the normal ranges provided by the central lab. Frequencies of each combination of shifts will be provided.

Potentially clinically significant (PCS) tables will also be used to summarize out-of-range values. Summaries will be given for any time post-baseline. The denominator for the percentages will be the number of patients with a result at the specific visits for each parameter.

All laboratory results will be listed, including scheduled and unscheduled/repeat measurements (if any). Laboratory assessments that are outside of normal ranges and/or with potential clinical significance will be flagged in the listings.

Clinically notable changes in LFTs will be summarized and listed for individual study subjects. The criteria for clinically significant LFT results are as follows:

- ALT $> 5 \times ULN$,
- AST $> 5 \times ULN$, or
- $TBL > 3 \times ULN$

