# 7.1.10.9. Safety Laboratory Assessments

Safety laboratory tests are summarized in [Table 2]. Clinical chemistry, hematology, coagulation tests, and urinalysis will be performed in all subjects at the scheduled visits shown in the Schedule of Assessments [Appendix 2]. At each visit, blood tests will be done after the completion of all study procedures except for study drug dosing and dispensing.

Confidential Page 60 of 115

**Table 2** Clinical Laboratory Tests

Panel/Assessments	Visits	Parameters to be Analyzed
Genotyping (Blood)	Screening – Part 1 only	APOE genotype
Immunology	Screening – Part 2 only	HIV-1/-2 Ag and Ab
		Hep B S Ag
		Hep C Ab
		HCV RNA (if applicable)
Clinical Chemistry	Screening – Part 2 only	HbA1c
		Vitamin B12
		TSH
		FSH (all females of non-childbearing potential only)
		hCG (all females of childbearing potential only)
Clinical Chemistry	Screening – Part 2,	Albumin
	Weeks 6, 13, 26, 39, 52, 65,	ALP
	78, and ET	AST
		ALT
		GGT
		TBL
		Direct bilirubin
		Indirect bilirubin
		Lactate dehydrogenase
		Blood urea nitrogen
		Creatinine*
		Glucose
		Magnesium
		Potassium
		Sodium
		Total protein
		Calcium
		Chloride
		Phosphorus
TT 4.1	G : D + 2	Uric acid
Hematology	Screening – Part 2,	Hemoglobin
	Weeks 6, 13, 26, 39, 52, 65,	Hematocrit RBC count
	78, and ET	
		RBC MCV White blood cell count with differential (percentage of neutrophils,
		lymphocytes, monocytes, eosinophils, basophils) Platelet count
Coagulation Tests	Screening – Part 2,	aPTT
Coagulation Tests	Weeks 6, 13, 26, 39, 52, 65,	PT
	78, and ET	INR for PT
Urinalysis	Screening – Part 2,	Color
Officialysis	Weeks 6, 13, 26, 52, 78,	
	and ET	Appearance pH
	and L1	Specific gravity
		Glucose
		Protein
		Ketones
		Blood
		Microscopic examination (RBC, white blood cells, epithelial cells,
		casts, crystals, bacteria)
		Urine pregnancy test (all females of child bearing potential only) at
		all visits except Screening – Part 2

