#### 10.10.2. Clinical Laboratory Evaluations

Clinical laboratory test results will be summarized and listed. Summary statistics for the CBL and the percentage out of range (normal reference range as established by the central laboratory) will be presented for each post-baseline time point.

Clinically notable changes in LFTs will be summarized and listed for individual study subjects. The criteria for clinically significant LFT results are as follows:

- ALT  $> 5 \times ULN$ ,
- AST  $> 5 \times ULN$ , or
- TBL  $> 3 \times ULN$

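### SAP 8.5.3 sends categorical laboratory results to listings only, which conflicts with the protocol and leaves no clearly specified by-arm table for qualitative urinalysis results

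*SAP*

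**What the plan says.** The laboratory text sits under an unnumbered subheading within SAP 8.5.3. In order, it says the following.

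- Scope: "Clinical lab results will be reported for hematology, clinical chemistry, coagulation tests, and urinalysis and will be summarized by visit".
- Numeric parameters are described by change and percent change from baseline. The next sentence is: "If a parameter is categorical, it will be listed only".
- Shift tables: "Each lab value will be assessed as low, normal or high based on the normal ranges provided by the central lab". Then: "Frequencies of each combination of shifts will be provided".
- PCS tables: "Potentially clinically significant (PCS) tables will also be used to summarize out-of-range values". On timing: "Summaries will be given for any time post-baseline".
- A later paragraph has every laboratory result listed.

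Elsewhere, SAP 8.1 has data summarized overall and by arm, and SAP 8.1.1 gives frequency and percentage for categorical variables.

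Protocol 10.10 says categorical safety data will be summarized with counts and percentages. Protocol 10.10.2 has laboratory results both summarized and listed. It promises "Summary statistics for the CBL and the percentage out of range" for each post-baseline time point, judged against the central laboratory's reference range. Urinalysis is one of the panels in Protocol Table 2 and is not excepted.

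**The concern.** Every laboratory result is listed under a separate sentence of the same SAP subsection. The word 'only' therefore adds something only if it removes tables for categorical parameters, and a programmer could reasonably build the outputs on that reading.

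Urinalysis is the panel most exposed, because much of it may be reported as categories. At stake is whether an imbalance in, say, urinary protein or blood shows up in a table by arm, or has to be found by reading subject-level listings. A second issue is timing. If the definition of an abnormal result and the layout of the table are left open until after unblinding, they become post hoc choices.

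**Working it through.** There is no plan figure to reproduce and no error rate or power involved. The check compares texts and counts lines.

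**1. Is there a conflict?** Taken literally, the listing-only rule gives zero tables for a categorical laboratory parameter. Four statements call for one:

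- Protocol 10.10: counts and percentages for categorical safety data.
- Protocol 10.10.2: percentage outside the reference range at each post-baseline time point.
- SAP 8.5.3, first laboratory sentence: urinalysis summarized by visit.
- SAP 8.1.1: frequency and percentage for categorical variables.

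SAP Section 5 gives reasons for its other departures from Protocol version 3.0 (the DAD scale and the imaging and fluid biomarkers). The documents give no reason for this one.

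**2. Do the other SAP outputs fill the gap?**

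- *Shift tables.* The three classes are low, normal and high. A result such as negative, trace or positive has no natural low class, and no normal/abnormal class is defined. The text does not say whether the listing-only sentence overrides these tables.
- *PCS tables.* The only laboratory limits given in the subsection are for ALT, AST and total bilirubin. None is given for urinalysis. The summaries are for any time after baseline, so they would not deliver the by-time-point percentage in Protocol 10.10.2. The denominator sentence nevertheless refers to specific visits, so the PCS rule is itself unclear.
- *Adverse events.* Protocol 7.1.10.9 sends clinically significant abnormal values that are unexpected changes from baseline to AE assessment, and SAP 8.5.2 tabulates treatment-emergent AEs by arm. This route depends on investigator judgment and covers only part of the abnormal results.

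**3. How many parameters are affected?** Apart from the pregnancy test, the urinalysis panel in Protocol Table 2 has 9 lines: color, appearance, pH, specific gravity, glucose, protein, ketones, blood and microscopy ("Microscopic examination (RBC, white blood cells, epithelial cells" and further elements, counted as one line). The table does not say which are reported as categories, so two assumptions bracket the answer:

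- Only color and appearance are categories: 2 / 9 = 22%.
- Everything except pH and specific gravity is a category: 7 / 9 = 78%.

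**4. Are the data there to tabulate?** Yes. Table 2 schedules urinalysis at Screening Part 2 and at Weeks 6, 13, 26, 52 and 78, plus early termination. A baseline and five scheduled post-baseline visits are available.

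**The case against.** The best defence is position. The listing-only sentence closes the paragraph on change from baseline. Read there, it may mean only that a categorical result has no change score. The shift and PCS paragraphs that follow carry no exception for urinalysis, and SAP 8.1 makes summaries by arm. Further, if the central laboratory supplies a reference for a dipstick result, an abnormal value could be classed as high and enter the shift table. If it supplies none, the out-of-range percentage in Protocol 10.10.2 cannot be produced for that parameter either.

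Much of this stands, and it rules out stronger readings that a reader might draw:

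- *That urinalysis results are never tabulated by arm.* The shift and PCS text can be read as covering them, and clinically significant unexpected changes reach the AE tables.
- *That most urinalysis parameters are lost.* This assumes a reporting format that the documents do not give; the range is 2 to 7 of 9 lines.
- *That 325 x 5 = 1,625 urine samples go without an arm summary.* The product is a ceiling that assumes every randomized subject attends all five visits, whereas SAP 4.1 expects about 17% dropout by Week 78. The same samples also yield pH and specific gravity, which are summarized if numeric.

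Importance is also limited. The laboratory safety endpoint in Protocol 4.2.1 names chemistry, hematology and coagulation, not urinalysis. Creatinine, blood urea nitrogen, albumin and serum glucose are in the chemistry panel and keep their summaries.

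The defence does not remove the conflict. It needs the reader to supply a limit on 'listed only' that the sentence does not state, and to supply a normal/abnormal rule that the SAP does not define. Protocol 10.10 also asks for counts whether or not a reference range exists.

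**Conclusion.** The point holds as a conflict of wording with a worse output on its literal reading. The rule departs from Protocol 10.10 and 10.10.2 and from the SAP's own scope sentence. For urinalysis parameters reported as categories, no by-arm table is clearly specified; the AE tables are the only clear route, and only for clinically significant unexpected changes. The size is 2 to 7 of 9 urinalysis lines (22% to 78%), resting on the two bracketing assumptions about reporting format.

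Severity is minor. Laboratory safety data are analyzed descriptively, so what is missing is a clearly specified table, not a test. Efficacy, alpha and sample size are untouched.

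**What to change.** Replace the listing-only sentence in SAP 8.5.3 with wording such as:

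> Qualitative urinalysis results that have a reference category will be tabulated by treatment arm as the number and percent abnormal at each post-baseline visit, with a normal/abnormal shift from baseline, and will also be listed. Parameters with no reference category (for example color and appearance) will be listed only.

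Add one sentence saying how the low/normal/high shift tables and the PCS tables apply to qualitative results, and confirm the reporting format with the central laboratory so that 'abnormal' is defined before unblinding. Because Protocol 10.10 covers all categorical safety data, the SAP should record the remaining listing-only parameters as a deliberate departure. SAP 8.5.5 already offers a model: it summarizes ECG interpretation categories by number and percent at each visit.

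The cost is SAP wording and one or two descriptive tables from data already collected.

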- Subject with confirmed clinically notable changes in liver function tests (LFT) may be withdrawn from the study. The criteria for abnormal LFTs are as follows:
  - $\circ$  ALT or AST  $> 8 \times ULN$ ,
  - $\circ$  ALT or AST  $> 5 \times$  ULN for more than 2 weeks, or
  - o ALT or AST  $> 3 \times$  ULN, and TBL  $> 2 \times$  ULN or PT  $> 1.5 \times$  ULN
- Weight loss: Subjects who are not intentionally dieting who show the following degree of weight loss on study drug:
  - $\circ$  Weight loss > 6% of body weight compared to baseline, and
  - Reaching BMI < 22 if  $\ge$  65 years of age; or
  - o Reaching BMI < 16 if < 65 years of age

**Note**: The ideal body weight and BMI cut-off criteria for those < 65 years of age or  $\ge 65$  years of age are based on a meta-analysis by Winter et al. (2017).

The reason for discontinuation must be recorded on the appropriate page of the electronic case report form (eCRF).

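### The notable-LFT summary uses different criteria from Protocol 5.5 and gives no per-arm count of the combined ALT/AST plus bilirubin or PT pattern

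*SAP*

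**What the plan says.** Three places define notable liver function changes.

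- **Protocol 5.5 (withdrawal).** "Subject with confirmed clinically notable changes in liver function tests (LFT) may be withdrawn from the study". Three alternatives follow: ALT or AST above 8x ULN; ALT or AST above 5x ULN for more than 2 weeks; or ALT or AST above 3x ULN "and TBL $> 2 \times$ ULN or PT $> 1.5 \times$ ULN".
- **Protocol 10.10.2 (analysis).** "Clinically notable changes in LFTs will be summarized and listed for individual study subjects". The criteria are ALT above 5x, AST above 5x, or TBL above 3x ULN.
- **SAP, Clinical Laboratory Evaluations** (an unnumbered subheading inside 8.5.3, whose own title concerns ARIA). It repeats the 10.10.2 sentence and then says "The criteria for clinically significant LFT results are as follows", with the same three single-parameter cuts.

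The same SAP text plans other laboratory displays. For the shift tables, "Each lab value will be assessed as low, normal or high based on the normal ranges provided by the central lab". In addition, "Potentially clinically significant (PCS) tables will also be used to summarize out-of-range values", with no thresholds given and denominators set parameter by parameter. All results, including unscheduled and repeat ones, are listed, and abnormal values are flagged there.

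On data collection, Protocol 7.1.10.9 says "Clinical chemistry, hematology, coagulation tests, and urinalysis will be performed in all subjects at the scheduled visits". Its Table 2 places ALT, AST, TBL and PT at Screening Part 2, Weeks 6, 13, 26, 39, 52, 65 and 78, and early termination.

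**The concern.** One label carries two definitions, and the one used for reporting lacks the only combined criterion and makes no use of PT. A subject can reach a state that the protocol names as notable, and as a possible ground for withdrawal, without entering the summary that carries that name.

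Safety and tolerability over 78 weeks is a primary objective. A reader of the study report would reasonably take the notable-LFT table to count what the protocol calls notable, and it would undercount. Screening exclusion 20 removes subjects with ALT or AST above 3x ULN or TBL above 1.5x ULN (apart from isolated hyperbilirubinemia in diagnosed Gilbert syndrome), so combined cases would generally have arisen on study, where a comparison by arm is of interest.

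**Working it through.** There is no stated figure to reproduce. The check compares two rules. All values are multiples of ULN. M is the higher of ALT and AST, B is TBL, and P is PT.

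**Rules**

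- Analysis flag (Protocol 10.10.2 and SAP): S = (M > 5) or (B > 3).
- Combined criterion (Protocol 5.5): C = (M > 3) and (B > 2 or P > 1.5).

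**Region missed outright: C true and S false**

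- S false means M ≤ 5 and B ≤ 3.
- Adding C gives 3 < M ≤ 5, B ≤ 3, and (B > 2 or P > 1.5).
- This splits into 3 < M ≤ 5 with 2 < B ≤ 3 at any PT, and 3 < M ≤ 5 with B ≤ 2 and P > 1.5.

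**Illustrative profiles (parameters not named are set to 1)**

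| Profile | Meets 5.5 combined criterion | Counted by analysis flag |
|---|---|---|
| ALT 4, TBL 2.5 | yes | no |
| ALT 5.0, TBL 3.0 | yes | no |
| AST 4, PT 1.6 | yes | no |
| ALT 6, TBL 2.5 | yes | yes, through ALT only |
| ALT 4, TBL 3.5 | yes | yes, through TBL only |
| ALT 8.5 alone | no (meets the 8x criterion) | yes |

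**The other two criteria in 5.5**

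- M > 8 implies M > 5, so S is true.
- M > 5 for more than 2 weeks also implies M > 5, so S is true. Only the duration goes unreported.
- The combined criterion is therefore the only one of the three that can be missed.

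**Do the other planned displays give the count?**

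- Shift tables classify each parameter separately as low, normal or high. They use neither ULN multiples nor pairs of parameters.
- The potentially-clinically-significant tables have no stated liver thresholds and no combination rule, so they cannot be assumed to cover the pattern.
- Listings show the values but give no count by arm.
- Disposition tables capture only those who left, and 5.5 says that such subjects may be withdrawn.
- Adverse event tables depend on the investigator judging the result clinically significant and on the term chosen.

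**How a comparable paired rule is treated.** The ECG criterion in Protocol 5.5 is also joint: QTcF above 500 msec and an increase above 60 msec. It is carried as a pair into Protocol Table 5 and SAP 8.5.5, except that above 60 becomes 60 or more. The combined liver criterion is not carried across.

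**The case against.** The strongest reply is that the SAP has done nothing irregular. It reproduces the three criteria in the protocol's own analysis section. Section 5.5 is a discretionary rule for individual subjects that requires confirmed changes, and a rule for withdrawing a person need not use the same cuts as a rule for summarising a group. This stands in part. The inconsistency lies inside the protocol, between 5.5 and 10.10.2, and the SAP inherits it. The shared label still needs reconciling, because the reporting set lacks the combined criterion.

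A second reply is that a case would not be hidden. This also stands. A reader might infer that a combined case could pass through the trial unseen, or that the notable-LFT table is blind to all combined cases. The documents support neither. ALT at 4x and TBL at 2.5x ULN would each be out of range and flagged in the listings. Clinically significant abnormal results that are an unexpected change from baseline are to be assessed as adverse events (Protocol 7.1.10.9). Reasons for early termination are tabulated (SAP 7.1). The safety management committee reviews laboratory data at least monthly, and the DSMB sees aggregate and individual safety data. Combined cases beyond 5x or 3x do enter the table. What is missing is narrower: a specified per-arm count of the pattern.

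A reader might also want every 5.5 criterion tabulated. That is not needed, since the other two already trip the 5x cut. The criterion of more than 2 weeks also cannot be derived reliably from scheduled draws 7 to 13 weeks apart (Week 6 to 13, then every 13 weeks).

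Finally, the documents give no rate for such events, and Protocol 2.4 reports no organ toxicity with long-term tramiprosate. The point therefore rests on the protocol's own decision to name this pattern, not on any claim that cases are expected.

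**Conclusion.** The concern holds in a limited form. Protocol 5.5 on one side, and Protocol 10.10.2 with the SAP on the other, define clinically notable LFT changes differently. Subjects with highest ALT/AST above 3x and up to 5x ULN, TBL not above 3x, and either TBL above 2x or PT above 1.5x are left out of the notable-LFT summary. Combined cases above the single cuts are counted without being identified as combined. No table is specified to give the combined count by arm.

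The size in subjects is unknown. It could be zero, and no range can be derived from the documents. No efficacy result or error rate is affected.

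Two assumptions matter. First, the criterion is read as ALT/AST above 3x together with either TBL or PT. If PT above 1.5x ULN were meant to qualify alone, the omitted group would be larger. Second, the unstated thresholds of the potentially-clinically-significant tables are not assumed to include the combination; if they do, the SAP need only say so. No judgement is made on which clinical threshold is right.

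**What to change.** - Reconcile Protocol 5.5, Protocol 10.10.2 and the SAP's Clinical Laboratory Evaluations text, either by aligning the definitions or by giving the withdrawal and reporting criteria different names.
- Add to that SAP text a per-arm count and a listing of subjects meeting the existing 5.5 combined criterion. Use post-baseline ALT, AST, TBL and PT from the same visit's blood draw, including unscheduled repeats. The same-draw rule must be written down because 5.5 sets no time window. The text should also say whether one sample suffices or confirmation is required, since 5.5 speaks of confirmed changes.
- Add no flag for the 8x or sustained 5x criteria.

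The cost is one derived flag, one table and one listing. Visits, samples, enrolment and alpha are unchanged, so this is a free improvement.
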